### 13.6 Analysis Populations

The study contains two treatment arms with subjects receiving either catheter ablation, with or without AAD therapy; or, AAD therapy alone. The following analysis populations will be used to complete the analyses of data:

**Intent to treat subject population (ITT):** The ITT subject population will include all subjects randomized, where subjects will be classified by the group to which they are randomized, regardless of the treatment received. For the ITT population, cross-over subjects will be included in the Control Group per randomization. Lost-to-follow-up and withdrawn / early termination subjects will also be included in the ITT population.

**Per protocol subject population (PP):** The PP subject population will include randomized subjects who satisfy the following criteria, according to the treatment actually received:

- **Test Group:** subjects who
  - have undergone RF ablation,
  - are treated with the study catheter (THERMOCOOL® Catheter Family)
  - are in compliance (no major protocol deviations) with the study protocol, and
  - have been treated for the study-related arrhythmia.
- **Control Group:** subjects who
  - have started an investigator-prescribed AAD and completed the dose-loading period (2 weeks),
  - have not undergone RF ablation,
  - are in compliance (no major protocol deviations) with the study protocol, and
  - have been treated for the study-related arrhythmia.

The analyses conducted in the PP population will be as treated analyses. Subjects who have undergone RF ablation will be included in the Test Group regardless of the original treatment assigned (original randomization). Thus, cross-over subjects will be included in the Test Group for PP analyses.

**Safety Population (SP):** The SP will include all subjects who have undergone insertion of an ablation catheter, either as Test Group or cross-over subjects; and, subjects who started an

investigator-prescribed AAD in the Control Group and did not initiate ablation therapy. Analysis of catheter-related complications will be limited to include only subjects who initiated ablation treatment (catheter insertion) - Test Group and cross-over subjects. Adverse drug reactions will be analysed overall for all the subjects who have taken investigator-prescribed AAD and analyzed separately for cross-over subjects, those in the Test and Control Groups (excluding cross-over patients).

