5. The recognized reasons for patients not doing well on drug therapy are as follows:
  - a. Patients failing to take the medication as prescribed – called “non-adherence”:
    - i. Missed days (drug holidays) – recurring disease symptoms or sudden drug-related side effects, if drug rebound effect, after resuming medication.
    - ii. Irregular timing, resulting in low concentrations of active drug at some points or too high concentrations of active drug when medication is taken at close intervals (may manifest as side effect problem).
    - iii. Medication dropout – patient takes no drug but does not share this information with his/her physician – unexpected disease progression.
  - b. Patient cannot tolerate medication, even if compliant with prescribed regimen (side effects):
    - i. Sensitivity to the prescribed AAD.
    - ii. Concurrent prescribed medications for other chronic diseases are contraindicated for the particular AAD prescribed.
6. When a subject complains to his/her Investigator about the medication and requests a cross-over to receive ablation, the Investigator will have little idea of the root cause of the subject's medication-related problem.

A cross-over management algorithmh could be used to help sort out disease progression issues from drug-related problems.

7. The following guidelines should be addressed by each investigator, prior to making a decision on a subject:

REASON TO INDUCE CROSS-OVER	REASON TO AVOID CROSS-OVER

 
1. Severe symptoms of AF in the absence of evidence that the subject was not taking the prescribed medication and consensus that further medication would be unsuccessful.
 
2. Severe side effects or AF symptoms, evidence of adherence to the prescribed AAD regimen, and no other drug options to which to switch the subject.
 
	
 
1. Evidence that the subject did not take the medications as prescribed and/or took concurrent incompatible medications for other chronic diseases – this subject should undergo Medication Managementi and then return to the hospital 3 weeks later for re-evaluation.
 
2. Evidence not sufficiently strong to merit cross-over, in the minds of the Investigator..
 

h A copy of this algorithm will be available to investigators in this trial as a reference guide to managing subjects with difficulties with their prescribed AAD.

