7. ANALYSIS POPULATIONS

The following analysis populations will be used to complete the analyses of data.

Cross-over subjects will be handled differently for each type of analysis population, as described subsequently. In general, subjects from the control group who have an ablation procedure after the primary endpoint is met will not be analyzed as cross-over.

Intent to treat (ITT) population: The ITT subject population will include all

subjects randomized, where subjects will be classified by the group to which they are randomized, regardless of the treatment received. For the ITT population, cross-over subjects will be included in the Control Group per randomization. Lost-to-follow-up and withdrawn/early termination subjects will also be included in the ITT population.

Per protocol (PP) population: The PP subject population will include randomized subjects who satisfy the following criteria, according to the treatment actually received:

- **Test Group:** subjects who
 - have undergone RF ablation,
 - are treated with the study catheter (THERMOCOOL[®] Catheter Family),
 - are in compliance (no major protocol deviations that has an impact on scientific value of the study) with the study protocol, and
 - have been treated for the study-related arrhythmia.
- **Control Group:** subjects who
 - have started an investigator-prescribed AAD and completed the dose-loading period (2 weeks),
 - have not undergone RF ablation,
 - are in compliance (no major protocol deviations that have an impact on scientific value of the study) with the study protocol, and
 - have been treated for the study-related arrhythmia.

All analyses conducted in the PP population will be as treated analyses. For descriptive tables and simple inferential models with fixed treatment effects subjects who have undergone RF ablation will be included in the Test Group regardless of the original treatment assigned (original randomization). Thus, cross-over subjects will be included in the Test Group for PP analyses. For more complicated inferential analyses, models will be applied where treatment itself is included as time-dependent covariate (see section 10.2 and 10.6.4). The approach described above applies for all tables which do not summarize data by visit (e.g. for time to event endpoints and other endpoints calculated overall per-patient). For summaries by visit and repeated measurement models, cross-over subjects will be completely excluded.

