10.6.3 Rhythm throughout 3 Years Follow-up

For this secondary endpoint, the following definition will be used:

- % subjects in sinus rhythm at a specific visit: This variable will refer to the data captured at the visit. Details will be defined when preparing analysis programs.
- % subjects with recurrent AF/AT at a specific visit: This variable will also refer to the time period after previous visit up to the visit analyzed (including data captured at the visit analyzed). A subject has recurrent AF/AT if AF or AT is documented at any TTM, Holter or ECG within this timeframe (additional observations of any other rhythms at the same TTM; Holter or ECG are allowed).

To analyze this secondary effectiveness endpoint, rhythm (% subjects in sinus rhythm, % subjects with recurrent AF/AT) throughout 3 years follow-up, the number of subjects and percentage of subjects in sinus rhythm and the number and percentage of subjects with recurrent AF/AT at each visit during the 3 year follow-up time will be summarized and listed by treatment group at each follow-up visit. The analyses will be performed in both ITT and PP populations. Cross-over subjects will be completely excluded in the PP population.

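### The PP rhythm table drops cross-over subjects even at visits before they crossed over, so PP Control at those visits is selected on a later, partly outcome-related event

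*SAP*

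**What the plan says.** Rhythm over three years is a listed secondary effectiveness endpoint (Protocol 10.2; SAP 2.2.1). SAP 10.6.3 defines it visit by visit: "subjects in sinus rhythm at a specific visit: This variable will refer to the data captured at the visit". Recurrent AF/AT is counted over the interval since the previous visit. On populations, SAP 10.6.3 states: "The analyses will be performed in both ITT and PP populations". SAP table 14.2.9 is accordingly planned for both.

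The two populations treat cross-over differently:

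- **ITT (SAP 7):** "For the ITT population, cross-over subjects will be included in the Control Group per randomization".
- **PP by-visit tables (SAP 7):** "For summaries by visit and repeated measurement models, cross-over subjects will be completely excluded". For rhythm, SAP 10.6.3 adds: "Cross-over subjects will be completely excluded in the PP population". Neither sentence keeps the visits that came before cross-over.
- **PP Control criterion (SAP 7; Protocol 13.6 has the same condition):** subjects must "have not undergone RF ablation", with no time point attached.
- **Protocol 13.6:** "Thus, cross-over subjects will be included in the Test Group for PP analyses". Protocol 13.12.3, on rhythm, has no exclusion of cross-overs.

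Two other places bear on the point. SAP 10.2 fits a PP Cox model in which a cross-over subject counts as control until cross-over and as ablation afterwards. SAP 7 also says that Control subjects ablated after reaching the primary endpoint are not treated as cross-overs. The list of changes in SAP 5.1 does not mention the by-visit exclusion.

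**The concern.** Take a Control subject ablated at month 20. At month 6 and year 1 that subject was on drug as randomized, yet the PP table leaves the subject out of those columns. Membership of PP Control at month 6 is thus decided by something that happens more than a year later.

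That later event is linked to the outcome being tabulated. The first ground for cross-over in Protocol Appendix B, item 7, begins: "Severe symptoms of AF in the absence of evidence that the subject was not taking the prescribed medication". Appendix B, item 4, argues, on assumptions it states, that extensive cross-over would leave a healthier and more adherent group on drug.

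The rule is also one-sided. Test subjects who recur and are re-ablated stay on their index schedule (Protocol 11.2.1), and SAP 7 does not exclude them. If later cross-overs have more AF, the PP table makes drug therapy look better than it was at those visits and understates any rhythm benefit of ablation in that table.

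**Working it through.** **Anchor in the plan.** The documents give no rhythm rates, so there is no rhythm figure to reproduce. The only relevant planning input is the 50% cross-over rate, and the sample-size section uses it consistently:

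- Control progression at 3 years: 0.5 × 25% + 0.5 × 5% = 15%, which is the 0.85 in the effect-size formula.
- Effect size: ln(0.1625 / 0.0513) = 1.153 (printed as 1.154 in the protocol and 1.1541 in the SAP, a negligible difference).
- Schoenfeld events, one-sided 0.025, 85% power: 4 × (1.960 + 1.036)² / 1.153² is just above 27, rounded up to 28. This matches the final look in the operating-characteristics table.

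**Subjects removed.** 0.50 × 161 = 80.5. About 80 of 161 Control subjects would be missing from every PP visit column, before any other PP exclusion. At a visit before anyone had crossed over, all 161 would have been on drug.

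**Bias at a visit.** Let c be the share of Control subjects on drug at that visit who later cross over, p_x their recurrence rate at the visit, and p_s the rate in those who stay on drug.

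- On-drug rate: (1 − c) × p_s + c × p_x
- Rate shown under SAP 7: p_s
- Shown minus on-drug: −c × (p_x − p_s)

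Example with assumed rates p_s = 30% and p_x = 50%, and c = 50%: the on-drug rate is 0.5 × 30 + 0.5 × 50 = 40%. The table shows 30%, which is 10 points too low.

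Understatement of PP Control recurrence, in points (differences are assumptions):

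| c | p_x − p_s = 0 | 10 | 20 | 40 |
|---|---|---|---|---|
| 10% | 0 | 1 | 2 | 4 |
| 20% | 0 | 2 | 4 | 8 |
| 30% | 0 | 3 | 6 | 12 |
| 50% | 0 | 5 | 10 | 20 |

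The percentage in sinus rhythm follows the same formula with its own difference and the opposite sign.

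**Change over follow-up.** The 50% row applies at a visit before any cross-over. If half of the eventual cross-overs have already been ablated, those still to cross are 25 of every 75 still on drug. Then c = 1/3, and differences of 10 to 40 points give about 3 to 13 points. When no further subject will cross, c = 0.

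**Internal consistency.** For the same subject over the same months, SAP 10.2 counts the time as control, while SAP 7 and 10.6.3 discard it.

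**The case against.** Several points on the other side stand.

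- **The ITT table is there.** A reader might infer that the rhythm result as a whole is distorted. It is not. ITT keeps cross-overs in Control at every visit, and at early visits, when few have crossed, ITT Control is close to the on-drug rate. After cross-over, ITT Control mixes in post-ablation rhythm, so neither version of table 14.2.9 shows on-drug rhythm throughout follow-up.
- **The SAP did not create the selection.** A reader might blame the departure from protocol 13.6. But the protocol's PP Control also requires no RF ablation, so it is restricted in the same way. The protocol would in addition have placed the cross-overs' drug-treated visits in Test. The SAP removes that misclassification; its own fault is that it discards usable visits and does not declare the change.
- **Direction is not certain.** Appendix B also allows cross-over for severe side effects, and its healthier-remainder argument is conditional.
- **Size is assumed.** The 50% is a planning rate, and the sponsor aimed to reduce cross-over below published rates.
- **Month 3 is a weak example.** Transtelephonic monitoring starts on Day 104, the last day of the month 3 window, and ECGs are collected only if done as standard of care. Month 6 and year 1 are better illustrations.
- **Consequence is limited.** Protocol 13.16 specifies descriptive statistics, and SAP 10.6.3 plans no test of rhythm.

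None of this justifies dropping visits at which the subject was receiving the assigned treatment.

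**Conclusion.** The concern holds for the PP rhythm table. At visits before cross-over, PP Control is selected on a later ablation that is partly outcome-related. The expected effect is to understate Control recurrence by c × (p_x − p_s): 5 to 20 points at the planned 50% cross-over and assumed differences of 10 to 40 points, 2 to 8 points at 20% cross-over, and zero if later cross-overs have the same rhythm as the rest. The actual cross-over share will be known from SAP table 14.1.7.1; the difference in recurrence cannot be derived from the documents.

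The documents do not support the stronger statement that PP Control consists only of subjects who never went on to ablation. SAP 7 does not count Control subjects ablated after the primary endpoint as cross-overs, so the exclusion sentence does not reach them, although the PP Control criterion read literally does. Those two lines need reconciling.

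The primary log-rank test and the ITT rhythm table are untouched. The SAP 7 sentence also covers repeated-measures models, and SAP 12.1 has a like exclusion for quality of life; those analyses are not assessed here. The correction is worth making because it is cheap and removes an avoidable inconsistency, not because a main conclusion depends on it.

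**What to change.** Amend the SAP before database lock:

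1. In SAP 7 and 10.6.3, count a cross-over subject in PP Control at every visit before the date of the cross-over ablation, in line with SAP 10.2. Exclude visits on or after that date, or show them in a separate after-cross-over row.
2. For by-visit tables, reword the PP Control criterion so that it requires no RF ablation before the visit in question. Without this, step 1 contradicts the population definition.
3. Reconcile that criterion with the SAP 7 sentence on Control subjects ablated after the primary endpoint.
4. Print n per group and visit in table 14.2.9.
5. List the departure from protocol 13.6 in SAP 5.1.

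The cost is SAP wording and one date condition in the programs. No new data are needed, because SAP 10.2 already requires the cross-over date. The downside is that Control numbers and case mix change from visit to visit, and selection remains at later visits, when those still on drug are increasingly those who will never cross over. A footnote to the table should say so.

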## 9.5 Subject Disposition

- **Enrolled Subjects:** subjects who sign the study informed consent form and are randomized.
- **Excluded Subjects:**
  - **Test Group:** subjects who are enrolled and randomized to ablation therapy but never undergo insertion of the THERMOCOOL ablation catheter.
  - **Control Group:** subjects who are enrolled and randomized to medication management (AAD) but never begin taking investigator-prescribed AAD and are ineligible for ablation therapy.
- **Discontinued Subjects:**
  - **Test Group:** subjects who are enrolled and randomized to ablation therapy, undergo insertion of the THERMOCOOL ablation catheter, but do not undergo further ablation therapy (i.e., no RF energy is delivered). These subjects will be categorized as ‘discontinued’ if therapy is not possible due to equipment failure or if their arrhythmia is determined, at the time of electrophysiologic study, to be a non-study arrhythmia, e.g. atrial flutter, instead of PAF under investigation.
  - **Control Group:** subjects who are enrolled and randomized to medication management and have started an investigator-prescribed AAD, but do not complete the dose-loading period (~ 2 weeks), for reasons other than a safety failure or if their arrhythmia is determined to be a non-study arrhythmia, e.g. atrial flutter.
- **Lost to Follow-up Subjects:** All subjects should be encouraged to return for protocol required office, clinic visit for evaluation during the study follow-up period. If a subject is unable to return for an office or clinic visit or unable to be contacted by telephone, 3 separate telephone calls should be made to obtain subject related safety information. All attempts should be documented in the source documents. If the subject does not respond to the 3 telephone calls, then the investigator must send a certified letter to the subject. If the subject does not respond to the letter, then the subject will be considered “lost to follow-up” for the current study visit. Subject contact must be attempted at each follow-up time point and if unable to contact the subject after 3 phone calls, the subject should once again be sent a certified letter. Only after failing to contact the subject at the final follow-up visit, the subject will be considered lost to follow-up and the study termination/end form will be completed in the individual case report form.

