Safety Population: The Safety Population will include all subjects who have undergone insertion of an ablation catheter, either as Test Group or cross-over subjects; and, subjects who started an investigator-prescribed AAD in the Control Group and did not initiate ablation therapy. Analysis of catheter-related complications will be limited to include only subjects who initiated ablation treatment (catheter insertion) either as Test Group and cross-over subjects.

Adverse drug reactions will be analyzed overall for all the subjects who have taken investigator-prescribed AAD and analyzed separately for cross-over subjects, those in the Test and Control Groups (excluding cross-over subjects).

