8. GENERAL ISSUES FOR STATISTICAL ANALYSIS

8.1 General Statistical Methodology

Descriptive summaries will be provided where appropriate for each of the primary and secondary variables. Tables in the ITT population will summarize data by randomized treatment, tables in the PP and Safety populations will summarize data by treatment actually received if not otherwise specified.

Primary and secondary effectiveness analysis will be conducted in the ITT and the PP populations. All safety data analyses will be performed in the Safety Population.

Health economic and QoL tables will be completed for the ITT population unless otherwise specified. According to the protocol it was planned to use the PP population for health economic and QoL tables, but this was changed to ITT population to perform the analysis based on the randomized treatment groups.

Continuous, quantitative, variable summaries will include the number of subjects (N) with non-missing values, mean, standard deviation (SD), median, minimum, maximum, and quartiles, unless otherwise specified.

Categorical, qualitative, variable summaries will include the frequency and percentage (where applicable) of subjects who are in the particular category. In general, the denominator for the percentage calculation will be based upon the total number of subjects in the study population for the treatment groups unless otherwise specified.

The baseline value will be defined as value entered to the screening/baseline page of the eCRF (terminology screening/baseline is not used consistently in eCRF, but there is only one screening/baseline assessment planned according to protocol).

All analyses will be performed using SAS[®] Software version 9.1.3 or later. ADDPLAN[®] version 5.0.2 or later and East version 5.3 or later may also be used.

For re-calculating of operating characteristics for the analyses of the primary endpoint, the software WinLD will be used.

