11. SAFETY AND TOLERABILITY ANALYSES

All safety end points will be presented by using the safety population.

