11.5 Adverse Drug Reactions

The number and percentage of subjects with adverse drug reactions defined as AE possibly, probably or definitely related to AAD will be summarized by system organ class and preferred term according to Test Group, cross-over group and Control Group (without cross-over subjects). The number and percentage of subjects with adverse drug reactions will also be summarized by causality, by anticipated or not, by severity and by outcome.

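### The Safety Population admits drug-treated subjects only through the Control Group, so a Test subject who takes an AAD but never has a catheter inserted is in no AE, SAE or ADR table

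*SAP*

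**What the plan says.** SAP 7 builds the Safety Population from two groups. The catheter route takes in "all subjects who have undergone insertion of an ablation catheter, either as Test Group or cross-over subjects". The drug route takes in "subjects who started an investigator-prescribed AAD in the Control Group and did not initiate ablation therapy". Protocol 13.6 has the same two routes, so the SAP carried the definition over.

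The next paragraph of SAP 7 describes the ADR analysis more widely: "Adverse drug reactions will be analyzed overall for all the subjects who have taken investigator-prescribed AAD", with separate results for cross-over, Test and Control subjects.

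The population for the outputs is fixed without exception. SAP 8.1 says "All safety data analyses will be performed in the Safety Population", and SAP 11 says "All safety end points will be presented by using the safety population". In SAP 15.1, every table from 14.3.1 to 14.3.7.3 is labelled Safety. In SAP 15.2, data listings 16.2.23 (adverse events) and 16.2.24 (SAE form) are on the ITT population.

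Protocol 9.5 names a disposition category of "subjects who are enrolled and randomized to ablation therapy but never undergo insertion of the THERMOCOOL ablation catheter". Protocol 13.6 describes the arms as "subjects receiving either catheter ablation, with or without AAD therapy; or, AAD therapy alone". Protocol 11.3 defines AADs broadly, including beta blockers and calcium channel blockers. Protocol 12.6.2 has AEs recorded from consent to the end of the study.

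**The concern.** The drug route depends on the arm as well as on taking the drug. A Test subject enters the Safety Population only if a catheter is inserted. If that never happens and the subject is managed on an AAD, the subject is drug-exposed, followed for AEs and randomized, but absent from the population used for all safety tables.

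ADRs are one of the two key safety endpoints in SAP 2.2.2. For these subjects, drug reactions and SAEs would be missing from the numerator, and the subjects themselves from the denominator. The SAP would also be inconsistent with itself, because its ADR sentence promises to cover every subject who took an investigator-prescribed AAD.

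**Working it through.** The plan states no figure on this point, so there is nothing to reproduce. The check compares who is admitted with who is promised.

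**Step 1. Apply the two routes to each kind of subject.** The ADR column applies the SAP 7 sentence as it stands.

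| Subject | Catheter route | Drug route | In Safety Population | In stated ADR set |
|---|---|---|---|---|
| Test, catheter inserted, AAD taken | yes | no | yes | yes |
| Test, catheter inserted, no AAD | yes | no | yes | no |
| **Test, no catheter, AAD taken** | **no** | **no** | **no** | **yes** |
| Test, no catheter, no AAD | no | no | no | no |
| Control, AAD started, no ablation | no | yes | yes | yes |
| Control, crossed over, AAD taken | yes | no | yes | yes |
| Control, no AAD, no ablation | no | no | no | no |

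Only the third row is outside the Safety Population and inside the stated ADR set. The two statements in SAP 7 agree only if that row is empty.

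**Step 2. Can the row be non-empty?** Protocol 9.5 foresees Test subjects without catheter insertion. Inclusion criterion 3 (Protocol 9.3) requires every subject to be eligible for drug treatment and to have already failed one or two drugs. Protocol 13.6 allows AADs in the ablation arm, and the AAD definition in Protocol 11.3 is wide. No section describes a Test subject managed on drugs alone; that is an inference from these provisions.

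**Step 3. Does another clause admit the subject?** SAP 8.1 summarizes Safety tables by the treatment received. That decides the column for a subject already in the population, not who is in it. SAP 10.3 describes the Control Group as those randomized to AAD therapy. The Per Protocol definition in SAP 7 is expressly tied to the treatment received, and the Safety definition is not. Taken literally, a Test subject on drugs alone could count as Control in the Per Protocol analysis and be absent from the safety tables.

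**Step 4. Scale.** The planned Test arm is 161 (SAP 6). Let f be the share never catheterised and a the share of those who took an AAD. Neither is in the documents.

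- Subjects affected = 161 × f × a
- f = 2% (assumed): 161 × 0.02 = 3.2, so at most about 3
- f = 10% (assumed): 161 × 0.10 = 16.1, so at most about 16

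These maxima need a = 1, meaning every uncatheterised Test subject took an AAD. With a = 0 the number is zero. Under the present definition the Test arm would contribute 161 − 3 = 158 subjects to the safety tables at f = 2%, or 161 − 16 = 145 at f = 10%. An exposure-based definition would restore only the AAD takers among the difference.

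**The case against.** The best defence is an as-treated reading. Safety tables are summarized by treatment received (SAP 8.1). SAP 9.1 plans a listing of the treatment assignment used for the Per Protocol and Safety analyses, so assignment there may differ from randomization. The Per Protocol part of SAP 7 also uses Control Group in an as-treated sense. On this reading, a Test subject on an AAD alone is a Control subject for safety, and the gap closes. The text leaves room for this, but nowhere says it, and the Safety definition lacks the wording that makes the Per Protocol definition as-treated. A programmer following the text would leave the subject out.

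A second defence is that the ADR sentence sits under the Safety Population heading and may mean all AAD takers within that population. That removes the contradiction but not the omission. If the sentence is instead a specific rule that overrides the general one, the ADR gap closes, but the AE and SAE tables still omit the subject and the ADR tables are still labelled Safety.

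Several stronger conclusions might be inferred, and the documents do not support them:

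- **That 3 to 16 subjects are lost.** That range counts all uncatheterised Test subjects at an assumed rate. Those who took no AAD would be outside an exposure-based population too.
- **That only the Test arm loses subjects.** Protocol 9.5 has a parallel Control category, subjects who never begin an AAD and are ineligible for ablation. They are outside the Safety Population as well. The asymmetry is confined to drug-exposed subjects left out by this wording.
- **That the omitted subjects are frailer.** Nothing in the documents shows this. A thrombus on transesophageal echocardiography (Protocol 11.2.1) may only postpone ablation, in which case the subject later enters by the catheter route, or may end study involvement.
- **That the events are hidden.** They stay in listings 16.2.23 and 16.2.24, and SAP 9.1 lists the reasons for exclusion from each population.

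**Conclusion.** As written, SAP 7 and Protocol 13.6 leave a Test subject who took an investigator-prescribed AAD without catheter insertion out of all AE, SAE and ADR tables. That conflicts with the SAP's own statement of whom the ADR analysis covers, and the alternative readings do not clearly repair it.

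The size is unknown. The upper bound of 3 to 16 rests on an assumed 2% to 10% of 161 planned Test subjects never catheterised, all of them taking an AAD; the true number may be zero. The events are listed but enter no rate. Protocol 13.16 makes the safety analysis descriptive, so no test depends on it. The effect is probably small, but the gap concerns a key safety endpoint and is easy to close.

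**What to change.** In SAP 7, define the Safety Population by exposure: all randomized subjects who had an ablation catheter inserted or took at least one investigator-prescribed AAD, whatever their assigned arm. Then:

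- show uncatheterised Test subjects as drug-treated in the AE, SAE and ADR tables, in their own column or by footnote;
- keep the restriction to catheter-inserted subjects for catheter-related complications;
- record the departure from Protocol 13.6, with the reason, in SAP 5.

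No new data are needed, since AEs are recorded from consent and Protocol 11.2.1 puts all cardiac medication on the eCRF. The cost is a short change to SAP 7, an entry in SAP 5 and a sparse extra group in some tables. Subjects who received neither treatment would still be outside the population, in either arm.
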